Goal-Directed Resilience Training (GRIT) is a hands-on experiential simulation and repeated practice that takes the person back to his/her earlier goal-directed experiences and then applies them to episodes of pain and suffering. The brain is inherently a simulation device where actual and simulated actions activate the same cortical areas (e.g. Decety & Grèzes, 2006). Goal-directed responding is inhibited by stimulus-guided responses to fear or pain. The restoration of goal-directed engagement and relatedness are natural capacities we have for pain control (Erpelding & Davis, 2013). This is the main focus of the training. Participants are asked to identify engagement and social relatedness (the goal-directed resources) from childhood or early adulthood, since these early years are formative, as well as examples from present time. They are asked to re-experience these in descriptions and sensations, then take these episodes into experiences of pain or trauma, thereby transforming these into resilience. This is accomplished through a manualized program consisting of four modules: engagement, social relatedness, transformation, and defining a good life. GRIT training is a small-group intervention consisting of 5-12 participants per group. We propose a pilot study of 20-48 participants or 4 groups with 2 intervention and 2 control conditions to be conducted in Atlanta. Up to eight (8) subjects beyond our goal of 40 will be added to make up for attrition. Individuals randomized to control condition will participate in the GRIT the training after post-assessment. Training extends over 4 weeks, consists of 90-minute biweekly visits, for a total of 8 visits.

**Outcome Measures.** To test hypotheses 1 and 2, outcome measures for GRIT training include focused pain-relevant symptom measures, adaptive functions measures, neurocognitive measures, and PACE, as listed in Table 2. List of outcome measures are provided in Appendix 1.

Table 2. Proposed Outcome Measures for GRIT Training

Focused Pain-Relevant Measures	
Pain Outcome Questionnaire (POQ), (20 items)	
PROMIS Pain Interference Short Form. (8 items)	
PROMIS Sleep Impairment (8 items)	
PROMIS Sleep Disturbance (8 items)	
Pain Catastrophizing Scale, (13 items)	
Chronic Pain Acceptance Questionnaire, (8 items)	[time to completion = 23 minutes]
Adaptive Functions Measures	
Physical Health: SF-36 Health Measure: physical & mental health, (36 items)	

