**Statistical Considerations**

Design. This is a balanced randomized block design. Twenty (20) to forty-eight (48) eligible and consenting participants from the Atlanta area will be identified from the cohort of research participants at the Football Players Health Study (FPHS) at Harvard University in Boston, MA. They will be selected based on answers previously given to specific FPHS survey questions listed below. They will undergo a pre-training test session and consequently be randomized with 1:1 allocation to either the Immediate GRIT training (ImT) intervention group or the Delayed (DeT) training control group. There will be two Immediate (ImT) intervention groups of 5-12 participants per training group and two Delayed training (DeT) control groups with 5-12 participants in each control group.

Outcome measures (c.f. Table 2). Sample Size and Power. This is a pilot study. Using focused pain-relevant or adaptive measures as outcomes with effect size (minimally detectable differences in weighted scores between the ImT experimental and DeT control group, scaled by pooled standard deviation) of 1, 2, 3, and 4, a regression model with treatment, age and block as effects and an overall 0.05 significance level, 20 participants per group yields an 0.80 statistical power.

For all analyses intent-to-treat principles will be adopted for those who drop out. Pre-treatment scores will be used to generate sampling frames consistent with a multiple imputation approach (Rubin, 1999) to determine post-treatment values.

Statistical Analyses. Summaries will rely on means, standard deviations for continuous variables and frequency and percentages for categorical ones. Univariate analyses for weighted scores and continuous variables groups comparisons will rely on t-tests (if normality assumptions are upheld) and/or non-parametric testing. Categorical variables will be compared using Chi-square/Fisher exact/McNamer testing. Multivariate analyses for the responses of scales/subscales weighted scores, factoring in covariates effects on interventions vs. control, age, block, pre-treatment scores, will use the Generalized Linear Mixed Modeling (GLMM) approach that will allow blocks as random effects and grant each subject their own intercept. All analyses will be conducted using SAS version 9.4

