#### **4. Randomization**

After pre-testing of the first 10-24 participants, they will be randomly assigned to either the Immediate ImT group (n=5-12) for immediate training or to the Delayed DeT control condition (n=5-12). The method of randomization is a balanced randomized block design with 1:1 allocation to either receiving the GRIT immediate ImT training intervention or the Delayed DeT control condition. A stratified permuted block design randomization scheme will be pursued with a variable but masked block size. A one–two stratification factors will be considered for selection from position played, age, and baseline severity of pain. The randomization protocol will further dictate inspection of balance of these factors between the two groups every ten recruited participants.

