#### **5. Intervention Training**

There will be two Immediate Training ImT groups of 5-12 participants per training group and two Delayed Training DeT control groups with 5-12 participants in each group. One Immediate ImT intervention group will be trained at one time for 4 weeks with 2 biweekly sessions, followed by post-testing. During this time the Delayed DeT group waits, since only one group can be trained at one time. The Delayed DeT group will receive training after waiting 4 weeks and a first post testing session. At the end of its training, the DeT group will receive a second post-testing session.

Training sessions will be held at the Morehouse School of Medicine in the Research Wing. There will be two 90-minute training sessions per week, taking place between 4-6pm on two days out of Mondays through Thursdays. The exact days and times of the training will be set in advance for each group, and will not be accommodating of individual schedules.

Should a participant miss a scheduled training session or be unable to complete a session in full, the attendance requirements are as follows:

Participants are allowed to miss 2 out of 8 sessions. They are also given the option to make up one or both sessions. They are allowed to make up a maximum of 2 sessions. If they miss a 3rd session, they are not allowed to make it up but can stay in the study. If they miss a 4th session, they will be terminated from the study. The content of the makeup sessions will follow the content of the modules: (1) introduction to concepts (2) illustrative examples (3) applications to own life with exercises. Makeup sessions will be one-on-one with the interventionist, and will last no more than 30 minutes. Participants will be compensated for makeup sessions as they are for group training sessions they attend.

If a participant attends but cannot complete a training session, it will be considered a missed session if they leave before the half-way time point (45 minutes). In this case the above policy regarding missed sessions will apply. If they leave the training session after 45 minutes, they may complete the rest of the session as a homework assignment, since homework

assignments are practiced at the end of each session. Participants will only be compensated for incomplete sessions if they attend for at least half (45 minutes).

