**Interventionist ([name], MPH)**

The interventionist will work with one group at a time and meet in small group sessions of no more than 10 twice a week. She will be trained by [name] in the application of the GRIT intervention and control conditions. She will be required to follow [name] method exactly in their implementation. Each intervention visit and control visit lasts for 90 minutes. Any participant concerns that arise that cannot be addressed in the session will be brought to the attention of the Co-PI and Project Manager.

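### GRIT is delivered in two shared ImT groups, but the analysis states no training-group term; if outcomes cluster by group, the standard error of the arm comparison is too small

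*Combined protocol and SAP*

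**What the plan says.** Experimental Design and Methods describes the delivery: "GRIT training is a small-group intervention consisting of 5-12 participants per group". Section 5, Intervention Training, adds: "There will be two Immediate Training ImT groups of 5-12 participants per training group". The two ImT groups are trained in successive waves. In each wave a DeT group waits untrained for the four weeks and is trained only after the first post-test (Experimental Design and Methods; section 7, Control Condition). The Interventionist role descriptions give a different upper limit on group size: staff "meet in small group sessions of no more than 10 twice a week". They also mention a control visit of the same length as an intervention visit.

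On analysis, Statistical Considerations states: "Univariate analyses for weighted scores and continuous variables groups comparisons will rely on t-tests", with non-parametric tests as the alternative. The multivariable model is a generalised linear mixed model with arm, age, block and pre-treatment score, which "will allow blocks as random effects and grant each subject their own intercept". No training-group term, ICC or design effect appears in the analysis text or the power statement.

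The analysis text does not define block. The Design paragraph says: "This is a balanced randomized block design". Section 4, Randomization, says: "A stratified permuted block design randomization scheme will be pursued with a variable but masked block size". One or two stratification factors "will be considered for selection from position played, age, and baseline severity of pain".

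**The concern.** Participants are randomised individually, but those in ImT are then trained together in one of two groups. Shared sessions, group dynamics and a common facilitator can make outcomes within a group more alike than outcomes across groups. Discussing participants' experiences within the group is part of the method (Risks/Assessment), so an ICC above 0 is plausible. DeT has no such source of correlation at the first post-test.

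An analysis that treats ImT participants as independent then overstates the information in that arm. The Project Title and Narrative presents the pilot as a test of efficacy, the Overview states arm-comparison hypotheses, and the power statement uses a 0.05 level. The arm contrast will therefore be read as evidence for GRIT, and one group that happened to go well or badly could be mistaken for a training effect.

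**Working it through.** **The plan's own figure.** The power statement gives 0.80 for 20 per arm at effect sizes of 1, 2, 3 and 4 SD. It does not reproduce. At 1 SD, two-sided 0.05, power is 0.885 (normal) or 0.869 (t, 38 df); at 2 SD and above it is about 1.00. That is a separate matter. What counts here is that the statement assumes independent participants.

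**What block can absorb.** Each wave has one ImT and one DeT group. An effect specific to one ImT group is therefore an arm-by-wave effect, which a wave intercept, fixed or random, leaves in the arm contrast. A permuted randomisation block also contains both arms and does not identify the training group. A subject intercept handles repeated measures on one person, not correlation between people. Only if each training group is a block does the model hold the needed term.

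**Inputs.** Two ImT groups of size m, with m = 10 at the target of 40 completers and a permitted range of 5 to 12; 2m untrained DeT participants; 1:1 allocation. Assumed, because the documents do not give it: residual (baseline-adjusted) ICC of 0.02, 0.05 or 0.10, in ImT only.

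**Formula**, with residual variance σ²:
- Variance of the ImT mean: σ²[1 + (m − 1)ICC] / (2m).
- Variance of the DeT mean: σ² / (2m).
- Variance of the difference under independence: 2σ² / (2m).
- Ratio of true to assumed variance: 1 + (m − 1)ICC/2. The standard error (SE) factor is its square root.

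Example, m = 10, ICC 0.05: 1 + 9 × 0.05/2 = 1.225, and sqrt(1.225) = 1.107.

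**Simulation check.** 20,000 null trials per cell: two waves, pre-post correlation 0.5 (assumed), group effect in ImT only, least squares of the first post-test on arm, wave, pre-score and age.

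| m | ICC | SE factor, formula | SE factor, simulated | Type I error | Type I error after correction |
|---|---|---|---|---|---|
| 10 | 0.02 | 1.044 | 1.046 | 5.9% | 5.0% |
| 10 | 0.05 | 1.107 | 1.113 | 7.8% | 5.1% |
| 10 | 0.10 | 1.204 | 1.224 | 10.6% | 5.5% |
| 5 | 0.02 | 1.020 | 1.023 | 5.5% | 5.1% |
| 5 | 0.05 | 1.049 | 1.054 | 6.2% | 5.2% |
| 5 | 0.10 | 1.095 | 1.112 | 7.3% | 5.3% |

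At ICC 0, type I error is 5.1–5.2%. A further simulation at m = 12 (12,000 trials per cell) gave 6.0%, 8.1% and 11.4%.

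**Other model forms** (type I error at ICC 0.02 / 0.05 / 0.10; the mixed models use 6,000 trials per cell, Monte Carlo error about 0.3–0.4 points, and n − 5 df):

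| Analysis | m = 10 | m = 5 |
|---|---|---|
| Mixed model, block = random wave | 6.2 / 7.0 / 10.5% | 5.3 / 6.5 / 7.7% |
| Mixed model, block = random training group | 4.4 / 5.5 / 7.0% | 4.0 / 4.0 / 5.4% |
| t-test, no stratification | 5.8 / 7.0 / 8.8% | 5.2 / 6.1 / 7.0% |
| t-test, stratified on baseline pain | 4.1 / 5.0 / 7.2% | 3.6 / 4.1 / 4.9% |

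The stratified rows assume two pain levels within wave and permuted blocks of 2. Under that same scheme the baseline-adjusted model still gives 6.3 / 7.7 / 10.7% at m = 10. A change-score model, standing in for a repeated-measures layout with a subject intercept, gives 5.8–6.3 / 6.5–7.1 / 9.4% at m = 10.

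**What a reported p-value would need to be.** Multiplying the t critical value on 4m − 5 df by the formula factor, the uncorrected p must be below 0.041 / 0.031 / 0.020 at m = 10, or 0.046 / 0.041 / 0.034 at m = 5, to stay below 0.05 after correction.

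**The case against.** The strongest reply is that the harm depends entirely on an ICC the documents do not give. At 0.02 the factor is only 1.02–1.04, and with groups of 5 the inflation is modest throughout. A manual, fidelity monitoring, one primary interventionist, individual make-up sessions and individual workbook exercises may all keep the ICC low. This stands, and the percentages above are not expected error rates. It does not justify leaving the assumption of zero unstated.

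Second, block might mean training group. If so, most of the concern falls away for the mixed model. That reading fits poorly with a randomised block design, in which each block holds both arms.

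Third, stratifying on baseline pain largely protects the t-test: only one of the six cells exceeds 5%. This is correct, but pain is only a candidate factor, and the baseline-adjusted model gains no such protection.

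Fourth, this is a pilot meant to gather preliminary data, and no single p-value is designated as decisive. That limits the consequence. But the documents also frame it as a test of efficacy with a significance level.

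Fifth, a correction based on assumed ICCs cannot be checked in this trial. This is true, and it is why the correction belongs in a sensitivity analysis rather than the main result.

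**Conclusion.** The concern holds, conditionally. The plan states no term for the ImT training groups, and its most natural reading leaves any group effect in the arm contrast. For a residual ICC of 0.02 to 0.10 with groups of 10, the baseline-adjusted standard error is too small by a factor of about 1.04 to 1.20, and type I error is about 5.9% to 10.6%. With groups of 5 the factor is about 1.02 to 1.10 and the error 5.5% to 7.3%. These figures assume clustering in ImT only and block read as the wave. They vanish at ICC 0 and shrink greatly if block means training group. The omission is certain from the text; its size is not, so confidence is medium. This should be corrected before analysis, but it does not undermine the design.

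**What to change.** In Statistical Considerations:

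1. Define block. If it means each training group, say so.
2. Keep the baseline-adjusted arm comparison at the first post-test as the main analysis. Beside its confidence interval and p-value, report a pre-stated sensitivity range with the standard error multiplied by sqrt(1 + (m − 1) × ICC / 2), using the actual mean ImT group size for m and residual ICCs of 0.02, 0.05 and 0.10.
3. State that a result which does not survive this range cannot be separated from a training-group effect, and that two ImT groups are too few to estimate the group variance.
4. Reconcile the session limit of 10 in the Interventionist descriptions with the 5–12 given elsewhere, since it affects m. Clarify what a control visit is; it may simply mean DeT's later GRIT sessions. Only if DeT does meet in groups before the first post-test, use sqrt(1 + (m − 1) × ICC) instead.

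The cost is SAP wording and a few lines of code, with no added participants. The downside is sensitivity intervals about 4–20% wider at m = 10 and 2–10% wider at m = 5. At m = 12 they are about 5–25% wider: sqrt(1 + 11 × 0.02/2) = 1.054 and sqrt(1 + 11 × 0.10/2) = 1.245. All rest on ICC values this trial cannot check.

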## IMPLEMENTATION STEPS

Study procedures for the GRIT intervention will be submitted to the Institutional Review Boards at MSM.

### 1. Recruitment & Screening

Recruitment and an initial round of eligibility screening of study participants for GRIT will be conducted at Harvard Medical School, the coordinating center of the Harvard Football Players Health Study (HFPHS). They have built a cohort of research participants through administering a First Health and Wellness Questionnaire (Q1) that included questions relevant to former players' experience of pain. The HFPHS will recruit for this study from this cohort of participants, whose verified eligibility and contact information is stored in the FPHS data repository (HMS protocol # 14-2691), and who have not opted-out of receiving study communications from the FPHS. This recruitment will be conducted by telephone and/or email.

Additional participants will be recruited into the HFPHS cohort through the Morehouse study team marketing the GRIT study in the Atlanta area. Morehouse may sponsor announcements in the local media and with football players' organizations in the greater Atlanta area that present information about this study alongside the greater HFPHS, and invite former players to participate in the HFPHS Q1 effort in order to be considered for this study.

Interested former players in the Atlanta area who are not yet enrolled in the HFPHS will be referred to contact the HFPHS using a GRIT study-specific email address, so that they take the Q1 survey and become part of the entire cohort of participants. They will be asked by FPHS to complete the Q1 questionnaire and thus become part of the HFPHS cohort.

These steps will be used for selection and eligibility screening of participants for GRIT:

1. Identify all former football players living in the Atlanta area from the HFPHS cohort, who are 65 years of age or younger (currently about 79 former players) who are interested in continued research participation.
2. Contact those former players by phone and/or email to invite them to participate in the study.
  - a. If players communicate via email and are interested, HFPHS will schedule a screening call with them.
  - b. If a player is reached by telephone and they are interested, they will be asked if they would like to go through the screening process at that time, or schedule another call in the future.

3. Potential participants will be screened on the telephone according to the HFPHS screening guide attached. Screening data will be recorded in the secure internal study portal hosted at HMS.
4. Once a potential participant has been deemed eligible to participate by HFPHS, and has expressed interest, HFPHS staff will ask for their consent to share their contact information with the researchers at MSM, so they may be contacted to arrange for final screening, enrollment, and pre-testing. They will be notified that there may be a delay of many weeks until their information is transferred and they are contacted by MSM, as MSM cannot begin scheduling consent, final screening, and pre-testing sessions for individual participants until they are able to begin doing so with a full group of 10-24 (5-12 for each group).
  - a. It will be discussed with them that they will undergo two final eligibility screens for suicidality and psychosis with MSM researchers, and that it's possible they may not qualify for the study at that point. If they do not qualify for the study, they will be compensated for their time with half the amount of the pre-testing session (\$25).
5. Once the MSM research team has access to a potential participant's contact information through the secure study portal, they will contact them by telephone to schedule their final screening, enrollment, and pre-testing session. The participants will be contacted as soon as their information is received by MSM researchers.

## **2. Consenting & Pre-Testing**

Subjects will first be consented by the MSM researcher, sign a HIPAA waiver, and then undergo the final two eligibility screening assessments for suicidality and psychosis. If they qualify for the study they will then participate in the pre-testing session.

The consenting staff member will go over the consent form that describes the study, the risk and benefits, confidentiality and data security, participant rights, and each participant will have his questions answered. If the potential participant agrees with the consent information, he and the consenting person sign and date the consent form.

If a participant scores high on psychosis or suicidality during the final screening, the following steps will be initiated: They will be referred to professional mental health services as a source of support. The Georgia Crisis and Access Line ([name]) will be offered to participant for assistance. The telephone resource is available 24 hours a day/ 7 days a week and offers licensed counselors to assist. Mental Health Action Plan in Appendix 8 outlines the steps that will be taken to keep the participant safe and obtain further emergency mental health evaluation and treatment.

If deemed fully eligible to participate in the study, the participant will then begin the pre-testing session with the tests listed in Table 2. The pre-testing session will also include asking the questions included in Appendix 5. No research procedure will take place prior to the informed consent and eligibility screening. Participants will be informed that they may skip answering any questions that make them uncomfortable, but that they may not skip all questions in any one individual test and if they do, they will be withdrawn from the study.

Participants will be given sufficient time to review the consent and opportunity to ask questions. We will not be enrolling patients that cannot participate in the informed consent. Legally authorized representatives are not involved in this study. There are no medical procedures involved in this study.

The pre-testing session will last 90-120 minutes after the consent process, and will include all of the assessments noted above in the Table 2 "Outcome Measures" list.

